4.5.2 Imatinib

Pharmacokinetic studies of imatinib in healthy volunteers and patients with CML, GIST, and other cancers show that orally administered imatinib is well-absorbed, and has an absolute bioavailability of 98% irrespective of oral dosage form or dosage strength [49]. Food has no relevant impact on the rate or extent of bioavailability. The terminal elimination half-life is approximately 18 hours. Imatinib plasma concentrations predictably increase by 2- to 3-fold when reaching steady state with 400 mg once daily administration.

Imatinib is approximately 95% bound to human plasma proteins, mainly albumin and α_1 -acid glycoprotein [50]. The drug is eliminated predominantly via the bile in the form of metabolites. The fecal to urinary excretion ratio is approximately 5:1 [51].

Imatinib is metabolized in the liver mainly by the cytochrome P450 (CYP) 3A4 or CYP3A5 and can competitively inhibit the metabolism of drugs that are CYP3A4 or CYP3A5 substrates. Interactions may occur between imatinib and inhibitors or induces of these enzymes, leading to changes in the plasma concentration of imatinib as well as coadministered drugs. Major induces of CYP3A4 and CYP3A5 activity may increase metabolism and decrease exposure to imatinib (e.g. carbamazepine, dexamethasone, barbituates, phenytoin, rifampin, and St. John's Wort). Concomintant CYP3A4 and CYP3A5 inhibitors should be administered with caution (e.g. cimetidine, erythromycin, clarithromycin, ketoconazole, itraconazole, cyclosporine, grapefruit juice).

Hepatic and renal dysfunction, and the presence of liver metastases, may result in more variable and increased exposure to the drug, although typically not necessitating dosage adjustment.

4.5.3 Ruxolitinib

Ruxolitinib inhibits Janus Associated Kinases (JAKs) JAK1 and JAK2 which mediate the signaling of a number of cytokines and growth factors that are important for hematopoiesis and immune function. JAK signaling involves recruitment of STATs (signal transducers and activators of transcription) to cytokine receptors, activation and subsequent localization of STATs to the nucleus leading to modulation of gene expression.

Ruxolitinib inhibits cytokine induced STAT3 phosphorylation in whole blood from healthy subjects with myelofibrosis patients. Ruxolitinib administration results maximal inhibition of STAT3 phosphorylation 2 hours after dosing which returns to near baseline by 10 hours in both healthy subjects and myelofibrosis patients.

The pharmacokinetics of ruxolitinib was evaluated in healthy volunteers in two doubleblind, randomized, placebo-controlled studies [52]. Ruxolitinib is rapidly absorbed after oral administration with maximal plasma concentration (C_{max}) achieved within 1 to 2 hours postdose. Based on a mass balance study in humans, oral absorption of ruxolitinib is estimated to be at least 95%. Mean ruxolitinib C^{max} and total exposure (AUC) increases proportionally over a single dose range of 5 to 200 mg. There is no clinically relevant changes in the pharmacokinetics of ruxolitinib upon administration with a high-fat meal, with the mean C_{max} moderately decreased (24%) and the mean AUC nearly unchanged (4% increase).

For pharmacodynamics evaluations, investigators have relied on measuring the levels of downstream targets of JAK signaling and assessing the change in inflammatory markers in response to therapy. In the initial phase I/II reported by Verstovsek and colleagues [53], maximal mean inhibition of *p*-STAT-3 expression ranged from ~40% at the lowest dose tested to >90% inhibition at the highest dose tested, and returned to baseline levels by 24 hours. A dose- and time-dependent reduction of phosphorylated STAT-3 was observed with ruxolitinib treatment and was repoted in patients with JAK2V617 and wild-type JAK2. Elevated baseline levels of IL-6, IL-ra, IL-8, MIP-1 β , TNF- α , and CRP were all dramatically reduced with ruxolitinib treatment in myelofibrosis patients.

In vitro studies suggest that CYP3A4 is the major enzyme responsible for metabolism of ruxolitinib. Ruxolitinib is the predominant entity in humans representing approximately 60% of the drug-related material in circulation. Two major and active metabolites were identified in plasma of healthy subjects representing 25% and 11% of parent AUC. These two metabolites have one-fifth and one-half of ruxolitini's pharmacological activity, respectively. The sum total of all active metabolites contributes 18% of the overall pharmacodynamics of ruxolitinib.

Following a single oral dose of $[^{14}C]$ -labeled ruxolitinib in healthy adult subjects, elimination was predominantly through metabolism with 74% of radioactivity excreted in urine and 22% excretion via feces. Unchanged drug accounted for less than 1% of the excreted total radioactivity. The mean elimination half-life of ruxolitinib is approximately 3 hours and the mean half-life of ruxolitinib + metabolites is approximately 5.8 hours.

4.6 Rationale for Study Design

4.6.1 Rationale for Capecitabine Dosage and Schedule

The dose of capecitabine approved by the US Food and Drug Administration (FDA) for both metastatic colorectal and breast cancer is 1250 mg/m2 given orally twice per day, usually separated by 12 hours for the first 2 weeks of every 3 week cycle.

The most common dose-limited adverse effects associated with capecitabine monotherapy are hyperbilirubinemia, diarrhea, and hand-footy syndrome. Myelosuppression, fatigue and weakness, abdominal pain, and nausea have also been reported.

Approximately 26% - 65% of breast cancer patients had their doses reduced by at least 20% in the clinical trials [54, 55]. For this reason, many investigators evaluated capecitabine at a lower starting dose of 1000 mg/m² twice daily and demonstrated similar efficacy to the approved dose and more favorable side effect profile with an incidence of dose reduction ranging from 16 to 34% in phase II trials [56, 57]. A meta-analysis of phase II/III trials comparing toxicity profiles between 1000 mg/m² twice daily (lower dose) and 1250 mg/m² twice daily (standard dose) capecitabine in breast cancer found that the 1000 mg/m² twice daily had a clinically meaningful and significantly better toxicity profile than the 1250 mg/m² twice daily regimen [58].

4.6.2 Rationale for Imatinib Dosage and Schedule

Imatinib has been the standard-of-care for patients with CML since 2001. In the original phase I trial investigating imatinib therapy, there was no maximum tolerated dose that was reached. Therefore, researchers chose 400 mg because it was a convenient, safe, and active dose. Cumulative complete response achieved in CML patients after 7 years of imatinib therapy is 87%. At 7 years, the overall survival rate is 86% and 94% if only CML-related deaths are considered. One of the key studies for imatinib is the International Randomized Study of Interferon Versus STI571 (IRIS) study, which was a phase III, randomized, openlabel trial that compared the standard-of-care at that time, which was interferon and low-dose cytarabine, with imatinib 400 mg daily in patients who had early chronic phase CML [59]. The study was clearly in favor of imatinib in response rates. The study did not show a survival advantage for imatinib because 90% of patients who were on the interferon and cytarabine arm crossed over to imatinib therapy after a median of 9 months.

The first rationale for higher imatinib doses can be explained by a clear dose-response relationship, which was shown in a phase I study where patients responded more when given higher doses of imatinib [60]. Second, some mutations of BCR-ABL can be overcome by high-dose imatinib. Specific mutations can still be mildly sensitive to imatinib, and in these cases, a dose increase may be effective. Third, studies have shown that the dose of 600 mg imatinib given to CML patients in the accelerated phase was independently associated with significantly better time to transformation and better survival, compared to patients who received imatinib 400 mg [61].

The key study investigating standard dose imatinib versus high dose imatinib is the Tyrosine Kinase Inhibitor Optimization and Selectivity (TOPS) trial, a prospective, open-label, randomized (2:1 ratio) phase III trial that studied the efficacy of imatinib 400 mg versus 800 mg in chronic phase CML patients [62]. In the intent-to-treat population, a significantly higher rate of complete cytogenetic response and major molecular response in the high-dose arm was recorded at 6 months. However, at 12 months, although the response rates were still higher than those of the standard dose arm, the differences were not significant.
In patients with advanced or metastatic GIST, who were treated with imatinib 400 mg once daily, mean plasma tough level (C_{trough}) was higher in patients who responded to treatment. A target threshold of >1,100 ng/mL has been defined [63-65]. These results are similar to results previously found in patients with CML [66-68].

We will use therapeutic drug monitoring (TDM) in this clinical trial with the hope of establishing exposure-response relationship.

4.6.3 Rationale for Ruxolitinib Dosage and Schedule

A phase I/II study of ruxolitinib was conducted in JAK2V617F-positive and –negative myelofibrosis patients at ascending doses starting at oral doses with a twice daily schedule of 10 mg, 15 mg, 20 mg, and 50 mg, and once-daily dosing at 25 mg, 50 mg, 100 mg, and 200 mg [53]. Ruxolitinib at 25 mg twice daily or 100 mg once a day was established as the maximum tolerated dose based on the dose-limiting toxicity of reversible thrombocytopenia. At 15 mg twice a day, ruxolitinib treatment was associated with sustained reductions of splenomegaly, resolution of constitutional symptoms, improvement in exercise tolerance and performance status, and meaningful weight gain. Durable improvements in symptoms and splenomegaly were seen in both JAK2-mutated and wild-type patients, and 52% of treated patients had a rapid objective response in splenomegaly >50% reduction for ≥ 12 months. Marked depression in the heightened expression of proinflammatory cytokines were seen with ruxolitinib treatment and correlated with improvement in night sweats, fevers, fatigue, weight loss, and pruritus. After 12 cycles of therapy, there was a mean maximal suppression of JAK2V617F allele burden by a modest 13% with ruxolitinib treatment.

Ruxolitinib was subsequently approved for the treatment of intermediate- and high-risk patients with myelofibrosis based on two randomized, phase III studies: COMFORT-I [69] and COMFORT-II [70]. In COMFORT-I, starting doses in the patients randomized to ruxolitinib were 15 mg twice daily for patients with baseline platelet counts of 100,000 – 200,000 and 20 mg twice daily for those with platelet counts >200,000. There was no protocol-mandated dose change for anemia. Grade 3/4 anemia was the most frequent hematolgic adverse event and was observed in 45% and 19.2% of patients in the ruxolitinib and placebo arms, respectively. Grade 3/4 neutropenia was observed in 7.1% and 2% of patients in the ruxolitinib and placebo arms, respectively. The most common nonhematologic adverse event seen with any grade in the ruxolitinib-treated group was diarrhea (23.2% compared with 21.2% in the placebo group). Overall, ruxolitinib was a well-tolerated drug.

Mesa et al. (Blood 2013) found that approximately 70% of patients who received ruxolitinib in COMFORT-I had a dose adjustment within the first 12 weeks of initiating ruxolitinib treatment. At week 24, 77% of patients with baseline platelet counts of 100,000 - 200,000and 39% of those with baseline platelet counts >200,000 had titrated to a reduced ruxolitinib dose relative to their starting dose. With longer-term follow-up (median 149 weeks), the mean dose over time in patients who continued on study was ~10 mg twice daily for patients starting at 15 mg twice daily and ~15 mg twice daily for those starting at 20 mg twice daily. In both COMFORT studies, ruxolitinib demonstrated marked and sustained clinical benefits in spleen size and improvement in symptom burden, and was generally well tolerated. Anemia and thrombocytopenia were the most frequent hematologic adverse events. The recommended starting dose of ruxolitinib is based on the platelet count (https://www.accessdata.fda.gov/drugsatfda_docs/label/2011/202192lbl.pdf).

4.7 Formulation, Packing, Handling, and Administration

4.7.1 Capecitabine

Capecitabine tablets should be swallowed whole with water within 30 minutes after a meal.

Capecitabine is supplied as biconvex, oblong film-coated tablets for oral administration. Each light peach-colored tablet contains 150 mg of capecitabine and each peach-colored tablet contains 500 mg of capecitabine.

Capecitabine should be stored at 25°C (77°F). Excursions permitted to 15°C to 30°C (59°F to 86°F). Keep tightly closed.

Care should be exercised in the handling of capecitabine. Capecitabine tablets should be cut or crushed. Procedures for the proper handling and disposal of anticancer drugs should be considered. Any unused product should be disposed of in accordance with local requirements, or drug take back programs.

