4.3 Study Drugs

4.3.1 Capecitabine

The cycle length will be 21 days, and 1000 mg/m^2 given orally twice per day, usually separated 12 hours apart, on Days 1-14 of a 21-day cycle. Capecitabine should be taken with water within 30 minutes after a meal.

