4.7.2 Imatinib

Imatinib should be taken with a meal and a large glass of water. Imatinib tablets should not be crushed. Direct contact of crushed tablets with the skin or mucous membranes should be avoided. If such contact occurs, wash thoroughly as outlined in the package insert.

If a dose is missed, patients should be advised to take their dose as soon as possible unless it is almost time for their next dose in which case the missed dose should not be taken. A double dose should not be taken to make up for any missed dose.

Imatinib can be dissolved in water or apple juice for patients having difficulty swallowing. The required number of tablets should be placed in the appropriate volume of beverage (approximatel 50 mL for a 100 mg tablet and 200 mL for a 400 mg tablet) and stirred with a spoon. The suspension should be administered immediately afer complete disintegration of the tablet(s).

Tablets come in 100 mg very dark yellow to brownish orange, film-coated tablets, round, biconvex with bevelled edges as well as 400 mg tablets with very dark yellow to brownish orange, film-coated tablets, ovaloid, biconvex with bevelled edges.

Imatinib should be stored at 25°C (77°F). Excursions permitted to 15°C to 30°C (59°F to 86°F). Protect from moisture. Dispense in a tight container.

Procedures for the proper handling and disposal of anticancer drugs should be considered.

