4.8.1 Capecitabine

Capecitabine is the oncology pro-drug of 5-fluorouracil (5FU). Capecitabine is administered orally and undergoes mainly hepatic metabolism where it is first biotransformed into 5'-deoxy-5-fluorocytidine (5'-DFCR) by carboxylesterases and subsequently to 5'-deoxy-5-fluorouridine (5'-DFUR) by cytidine deaminase. Metabolism of capecitabine involves different enxymes, where thymidine phosphorylase converts 5'-DFUR to the active drug 5FU [71].

Concentration levels of capecitabine and both 5'-DFCR and 5'-DFUR are measured in PK studies [72]. Several PK studies were assessed previously in serum for capecitabine, where t_{max} ranged from 0.5 to 2 hours, with a C_{max} of 5000-9500 ng/mL and $t_{1/2}$ of 34-50 min. After the administration of a standard dose of capecitabine, it might be expected serum concentrations within 5-10,000 ng/mL.

Dosage: Capecitabine 1000 mg/m² given orally twice daily, separated 12 hours apart, on Days 1-14 of a 21-day cycle, to be taken with water within 30 minutes after a meal.

Sampling: Based on a 21-day cycle, as mentioned above, peak levels will be measured 2 hours after administration of capecitabine on day 1 and cycle 1 day 8.

Sample Handling: Peripheral blood will be collected in a tube containing 500 nM tetrahydrouridine (THU) to avoid *ex vivo* conversion of 5'-DFCR to 5'-DFUR [73] and will be allowed to clot for 30-60 min followed by centrifugation at 3000 rpm, 4°C, for 10 min.

Sample Storage: Serum samples will be stored at -80°C.

Extraction: Capecitabine will be extracted from the serum samples using the above mentioned protein precipitation extraction procedure. Minimum volume of blood sample considering duplicates for TDM (and PK) studies should be no less than 300 μ L (120 μ L is needed for one extraction).

Quantification: Concentration of capecitabine will be measured by a New York State Department of Health (and thereby CLIA-) approved LC-MS/MS assay developed for the

simultaneous quantification of OncoTreat-prioritized drugs. The method is based on an existing New York State DOH-approved assay for imatinib developed by CPTL for its clinical services, with only minor modifications.

Target Range: The target ranges for peak levels will be 5,000 - 10,000 ng/mL for capecitabine in serum.

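### Section 4.7.1 gives two incompatible instructions for capecitabine tablets: swallow them whole, and cut or crush them

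*Combined protocol and SAP*

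**What the plan says.** Section 4.7 is the part of the protocol that tells staff how each study drug is supplied, stored, handled and given. Its capecitabine subsection, 4.7.1, has four short paragraphs.

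- The first is about taking the drug: "Capecitabine tablets should be swallowed whole with water within 30 minutes after a meal".
- The second describes the tablets and their strengths.
- The third gives storage conditions.
- The fourth is about handling and disposal. It asks for care in handling the drug and then says: "Capecitabine tablets should be cut or crushed". It then turns to the handling and disposal of anticancer drugs and of unused product.

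Two other sections say how capecitabine is taken. Section 4.3.1 says "Capecitabine should be taken with water within 30 minutes after a meal". The dosage line in section 4.8.1 says "to be taken with water within 30 minutes after a meal". Neither mentions whole, cut or crushed tablets.

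**The concern.** The two sentences concern the same tablets in the same subsection, and one rules out the other. This is working text, not background: section 4.7 is where a pharmacist or research nurse would look to learn what to do with the tablets and what to tell the subject.

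What is at stake is the safety of the subject and of whoever handles the tablets. The protocol asks for care in handling this drug and then, in the next sentence, gives an instruction that conflicts with its own administration instruction. Two people who each follow one sentence of section 4.7.1 would do different things, and each could cite the protocol.

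**Working it through.** No arithmetic applies, and there is no stated figure to reproduce. The check is a comparison of text.

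**Step 1: the sentences side by side.**

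| Place | Text | What it says about the tablet |
|---|---|---|
| 4.7.1, first paragraph | "Capecitabine tablets should be swallowed whole with water within 30 minutes after a meal" | Swallowed whole |
| 4.7.1, fourth paragraph | "Capecitabine tablets should be cut or crushed" | Cut or crushed |
| 4.3.1 | "Capecitabine should be taken with water within 30 minutes after a meal" | Silent |
| 4.8.1, dosage line | "to be taken with water within 30 minutes after a meal" | Silent |

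**Step 2: can both sentences be followed?** Both could stand if each were tied to its own circumstances, for example one rule for most subjects and another for those who cannot swallow tablets. Section 4.7.1 contains no such condition. The imatinib subsection, 4.7.2, does make this kind of provision: it states "Imatinib tablets should not be crushed" and separately describes dispersing the tablet in a drink for patients who have trouble swallowing. Section 4.7.1 has nothing comparable, so the two sentences apply to the same tablets at the same time and cannot both be followed.

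**Step 3: does any other text decide?** Sections 4.3.1 and 4.8.1 are silent. The pharmacology text in section 4.5.1 deals with dose, food and renal function, not with whether the tablet is intact. Footnote o to the study calendar (Table 6) has subjects take the dose under the direction of clinic staff on PK sampling days. That leaves the answer to staff who are working from the contradictory section. Nothing in the documents resolves the conflict.

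**Step 4: how often and for how many?** Section 4.3.1 has capecitabine taken twice a day on Days 1 to 14 of each 21-day cycle, so the instruction is relevant on 2 × 14 = 28 occasions per cycle for a subject on full dosing. The number of such subjects is not given. Section 12 uses 9 as the minimum number expected to be treated, over all agents together. Section 4.2 caps Part 2 at 30, again over all agents. Section 2.2.2 expects only a very small number on any single drug.

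**Step 5: is any statistical quantity affected?** No. The sample size, power, alpha and response-count threshold in section 12 do not depend on how tablets are handled.

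**The case against.** The strongest reply is that this is a slip of one word, that the second sentence belongs to a handling paragraph rather than to the dosing directions, and that a sensible reader would follow the explicit opening instruction.

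Part of this stands. The second sentence does sit in the handling and disposal paragraph and is not clearly a direction to the patient. A word may have been lost, either in the source or when the text was read from PDF. However, the surrounding prose reads as intact, and the documents cannot show whether anything is missing. The section's own heading covers handling as well as administration, so the conflict remains whichever label the sentence carries. It should not be left to each reader to decide which sentence to ignore.

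A reader might also infer more than the documents support:

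- **An effect on the PK data.** Section 4.8.1 measures a 2-hour peak against a target range of 5,000 to 10,000 ng/mL, and section 4.1 lets PK results inform dosing. It is tempting to say that crushing would shift that peak. No part of the documents says that cutting or crushing changes capecitabine absorption or its peak level, so the point does not rest on this.
- **An effect on every capecitabine subject.** That would assume that each subject is actually given the wrong direction. The documents show only that each could be.
- **That the right answer is obvious.** The negated imatinib sentence in 4.7.2 concerns a different drug and does not establish what was meant for capecitabine.
- **An error carried into a patient diary.** Diaries appear only in the general list of source documents in section 11.6. No capecitabine diary is described.
- **A flaw in the design.** This is an inconsistency of wording. No design decision turns on it.

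**Conclusion.** The contradiction is real, and the text is wrong as written: two sentences of section 4.7.1 cannot both be followed, and no other section decides between them. It merits correction because it is operative text about handling and taking an anticancer drug.

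Its reach is limited. It touches one of the three study drugs named in section 4.3, for a number of subjects that is unknown and probably very small. The documents show no effect on an endpoint or an analysis, and no statistical figure changes.

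The conclusion assumes that the text as read from the PDF matches the source. If the source reads differently and the two sentences agree there, the point falls away. Which instruction is correct is a clinical and pharmacy matter for the sponsor, and this review takes no position on it.

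**What to change.** The sponsor should compare both sentences of section 4.7.1 with the source document and reconcile them so that the subsection gives one consistent instruction. If both were meant to apply in different circumstances, the text should state those circumstances. Any dispensing or patient instructions derived from this section should then be checked against the reconciled text.

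The protocol change is a word or a sentence. It needs no recalculation and no change to the analysis. Whether derived materials carry the same wording cannot be seen from the documents, so the effort of correcting them is unknown.
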